3.2.2 Secondary Study Endpoints

- DLQI score of ≤1 (no impact on HrQOL)
- Achievement of a Minimal Clinically Important Difference (MCID) on the DLQI
- Concomitant topical psoriasis treatment
- Concomitant oral and biologic psoriasis treatment
- Patient reported time spent on phototherapy
- Patient reported time and cost associated with travel for phototherapy treatments
- Change in the product of BSA times PGA relative to baseline (BSAxPGA). See Appendix B for BSA tool.
- Duration of treatment response during observation period
- Phototherapy number and dose

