8.2 Secondary Endpoints

In addition to pooled analyses described above, separate analyses will be conducted for each skin type using a non-inferiority margin of 15%. The estimated risk difference in dichotomized DLQI at week 12 and PGA at or before week 12 will be estimated empirically based on the proportion of patients achieving the endpoint in each skin type sub-group and study arm. We will also assess heterogeneity of treatment effect (HTE) across the three skin types using logistic regression. In this analysis, we will fit models for each of the two primary outcomes with skin type, treatment arm, and their interaction as predictors. HTE will be assessed using an omnibus Wald test of all interaction regression parameters for each outcome of interest in order to minimize multiple testing and consequent alpha inflation.

In secondary analyses, we will investigate additional outcomes:

- Total number of phototherapy treatments received
- Cumulative dose of phototherapy
- Frequency of topical concomitant psoriasis treatment
- Changes in initiation, dosing, or discontinuation of oral or biologic psoriasis treatments
- Patient-reported amount of time spent on phototherapy
- Patient reported travel (cost and time)
- DLQI score of ≤1at week 12

- MCID on DLQI at week 1245
- Physician reported change in the product of body surface area (BSA) times PGA (both as a continuous measure and as a dichotomous measure evaluating a 75% and 90% reduction in the BSAxPGA).
- Duration of treatment response
- Percentage of patients receiving ≥ 80% of assigned treatments

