Because we have no a priori hypothesis of equivalence between treatment arms on these outcomes, these analyses will be conducted using standard hypothesis testing principles. We will report the mean (for continuous measures) or frequency (for binary measures) and 95% CIs for each measure within treatment arms as well as the difference in means or frequencies between treatment arms and the 95% CI of the difference. Secondary outcomes will be measured with a frequency as described in Appendix D, Schedule of Study Procedures. We will analyze these measures using linear or logistic regression models with robust variance estimators via Generalized Estimating Equations (GEE) to account for within-patient correlation that occurs with repeated measures. Regression models will include terms for treatment arm, time since randomization (categorical), skin type, and the treatment arm/time interaction. Inclusion of the interaction term will allow us to assess possible variation in effectiveness of home phototherapy relative to office-based phototherapy over time. Physician reported outcomes (PGA times BSA) will be measured at baseline and at the earlier of week 12 or upon discontinuation of phototherapy, whichever comes first. We will compare this outcome between home and office-based phototherapy arms using linear regression adjusted for skin-type. All secondary analyses will be repeated within each skin type stratum.

During the follow-up observation period, weeks 13-24 after start of therapy, we will compare dichotomized DLQI, and receipt of concomitant topical psoriasis treatment between study arms. These measures will be assessed every four weeks during the observation period and analyses will use the same approach as described above for other secondary outcomes. We will also assess change in oral or biologic psoriasis treatment during the observation period at week 24.

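### Section 8.2 does not say whether the continuous BSA x PGA change is absolute or percent; if it is absolute, leaving the baseline product out of the model costs precision

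*Combined protocol and SAP*

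**What the plan says.** Section 3.2.2 lists the endpoint as "Change in the product of BSA times PGA relative to baseline". Section 8.2 lists it as "Physician reported change in the product of body surface area (BSA) times PGA (both as a continuous measure and as a dichotomous measure"; the dichotomous versions are reductions of 75% and 90%. On timing, "Physician reported outcomes (PGA times BSA) will be measured at baseline and at the earlier of week 12" or discontinuation of phototherapy. On the model: "We will compare this outcome between home and office-based phototherapy arms using linear regression adjusted for skin-type". On reporting: "We will report the mean (for continuous measures) or frequency (for binary measures) and 95% CIs for each measure within treatment arms", together with the difference between arms and its interval. On inference, "these analyses will be conducted using standard hypothesis testing principles".

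No section names a baseline covariate, a transformation, or a rank-based or robust alternative for this comparison. The robust variance estimators in section 8.2 are attached to the GEE models for repeated measures. Section 4.1 requires a PGA average above 1.0, and neither 4.1 nor 4.2 limits BSA. Section 6.1 collects both PGA and BSA at baseline. Section 3.1.4 stratifies randomization on clinic and skin type, not on extent of disease. Section 8.3 gives no SD or power for this outcome.

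**The concern.** The text allows two readings of change, and they behave differently in a linear model. An absolute change is bounded by the starting value, so it is large in patients with extensive disease and small in the rest. With no upper BSA limit, a right-skewed baseline is plausible. Neither the stratification nor the model then removes the part of the variation that comes only from where patients started. A percent change largely avoids this.

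At stake is the precision of the only continuous physician-rated effectiveness outcome. It is tested by ordinary hypothesis testing, so an unnecessarily wide interval could hide a home-office difference. A scale left open until the data are seen also leaves a choice that should be made beforehand.

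**Working it through.** **1. The plan's own figure.** The only sample-size calculation (section 8.3) is for the binary primary outcomes: n per arm = (1.960 + 0.842)² x (0.5x0.5 + 0.5x0.5) / 0.15² = 7.85 x 0.5 / 0.0225 = 174.4, so 175. It reproduces, but says nothing about BSA x PGA.

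**2. The two readings.** Illustration, with assumed values: patients at 4% and 40% BSA, both with PGA 2, start at products of 8 and 80. If each loses half, the absolute changes are 4 and 40, and the percent changes are 50% and 50%. On the absolute scale one patient's change is ten times the other's.

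**3. Cost of omitting baseline.** If baseline correlates ρ with the absolute change, adding it multiplies the variance of the arm difference by about 1 - ρ². If the adjusted analysis had 80% power, the unadjusted one has Φ(2.802 x √(1 - ρ²) - 1.960):
- ρ = 0.5: 2.802 x 0.866 - 1.960 = 0.47, power 68%
- ρ = 0.7: 2.802 x 0.714 - 1.960 = 0.04, power 52%
- ρ = 0.9: 2.802 x 0.436 - 1.960 = -0.74, power 23%

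**4. Simulation.** Every distributional input is an assumption: BSA log-normal with median 6-8% and log-SD 0.5 to 1.1; PGA 1.33 to 4; median 25% of baseline remaining; log-SD of response 0.6, 1.0 or 1.4; home arm with 25% more residual disease; two-sided 0.05; robust standard errors; 400 trials per setting (Monte Carlo error up to √(0.25/400) = 0.025 in power). Variance with baseline added, as a fraction of the plan's:

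| Baseline BSA | N | Response SD 0.6 | 1.0 | 1.4 |
|---|---|---|---|---|
| median 6%, log-SD 0.3 (low-skew check) | 1050 | 0.46 | 0.82 | 0.92 |
| median 6%, log-SD 0.5 | 350 | 0.30 | 0.68 | 0.85 |
| median 8%, log-SD 0.8 | 350 | 0.18 | 0.53 | 0.73 |
| median 8%, log-SD 1.1 | 350 | 0.15 | 0.47 | 0.69 |

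At N = 1050 the range over log-SD 0.5-1.1 was 0.15-0.86. Power there ran 0.24-0.75 for absolute change on arm and skin type, and 0.31-0.995 with baseline added; in the middle case (median 8%, log-SD 0.8, response SD 1.0) it was 0.42 and 0.60. The direction was the same at N = 780 (350 + 350 + about 80, from section 3.1).

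**5. Is this an artefact of a proportional effect?** With a constant 1.5-unit excess in the home arm instead, the variance ratio was 0.11-0.83, power 0.11-0.85 without baseline and 0.14-1.00 with it. The loss does not depend on a multiplicative effect.

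**6. Influence.** The 5% of patients with the largest residuals carried 43-67% of the residual sum of squares (36-43% in the low-skew check). Under normality the share is 2 x (1.96 x 0.0584 + 0.025) = 28%.

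**7. Error rate.** With no arm difference, rejection was 0.050-0.058 with or without baseline.

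**8. Percent reading.** Percent change on arm and skin type had power 0.89 in the middle case, against 0.95 for a baseline-adjusted log model. In a separate assumed set-up at 525 per arm, adding log baseline to the percent-change model left the standard error unchanged to three decimals and power within 1 point.

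**The case against.** The strongest reply is that percent change may already be meant. The endpoint in section 3.2.2 is framed as relative to baseline, and section 8.2 puts the continuous version in one bullet with the 75% and 90% reductions, which are relative. On that reading the problem largely disappears. This stands, and it is why the request is first to state the scale.

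It can also be said that this is one of many secondary outcomes with no stated power, that the 75% and 90% reductions limit the influence of extensive disease, and that section 8.4.1 will describe baseline imbalance with intervals. This stands too, although describing an imbalance does not adjust for it.

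Three stronger readings are tempting but unsupported.
- A reader might infer that the arm difference depends mostly on which arm holds more patients with extensive disease. In one simulation at 525 per arm and log-SD 1.0, adding baseline took the standard error from 2.27 to 1.78. The variance ratio is (1.78/2.27)² = 0.61, so baseline accounts for about 39%. A majority share arises only under some of the assumed settings.
- The same figures invert to 1/0.61, about 1.6 times the patients. That is one assumed case, not a property of this trial.
- A reader might expect the loss to be worse within skin types. At N = 350 the variance ratios were 0.15-0.85, much the same as at N = 1050. Intervals are wider there because there are fewer patients, not because omitting baseline costs proportionately more.

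**Conclusion.** The point holds in limited form. Section 8.2 leaves the scale of the continuous BSA x PGA change open and omits a baseline value the trial already collects. If the change is absolute, this loses precision and gives patients with extensive disease strong influence. Adding baseline brings the variance to roughly 0.15-0.86 of the plan's under assumed right-skewed baselines. The saving can fall to 8% (ratio 0.92) when low skew goes with a very variable response. These ranges rest on distributions that the documents do not give.

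A reader might infer bias or excess false positives. Neither follows: randomization keeps the estimate unbiased, and simulated type I error stayed near 5%. If the change is percent, what remains is an unclear definition. The co-primary outcomes and their conclusions are not touched, so this is a minor improvement.

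**What to change.** In section 8.2, state whether the continuous BSA x PGA outcome is absolute or percent change, and match section 3.2.2 to it.

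- If absolute: fit arm, skin type and baseline BSA x PGA. Optionally add a relative-scale analysis (percent change, or the log of the product plus 1, which handles zeros) to match the 75% and 90% reductions. The choice between percent and log is not settled by this check. The middle case above favoured log (0.95 against 0.89), while another simulation at 525 per arm favoured percent (80-82% against 61-65%). Name one beforehand.
- If percent: say so. A baseline term is then optional and adds little.

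The cost is SAP wording. No new data, visits or patients are needed.

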3.1 General Design

The design is a large pragmatic randomized active comparator study of home vs. office based NB-UVB phototherapy for the treatment of psoriasis. Both comparator treatments are considered standard of care and thus this would be classified as a Phase IV study. Dosing of phototherapy will be based on a standardized protocol (see APPENDIX A) or a standard protocol that is routinely used by the local investigators in order to reflect routine clinical practice. The study will include up to 1050 patients stratified by Fitzpatrick skin type (350 skin type I/II, 350 skin type III/IV, we anticipate that approximately 80 participants will be enrolled in Skin type V/VI). We hypothesize that home phototherapy will be noninferior to office based phototherapy. There will be a recommended screening period of up to 28 days, to allow for obtaining informed consent and administrative procedures necessary for office based or home phototherapy, as well as randomization. Patients will be randomized (1:1) to home vs. office-based phototherapy within 28 days of the baseline visit or per standard of care of individual practices. If the patient is randomized to home phototherapy a machine will be delivered to their home and phototherapy treatment initiated within 14 days of randomization. If the patient is randomized to office phototherapy, the first treatment should occur within 14 days of randomization. The patient will be assessed by the dermatologist (or PA or NP or other gualified clinician as appropriate to the clinical practice) at baseline and at 12 (plus or minus 2) weeks after start of phototherapy, or at the time of discontinuation of phototherapy, whichever comes first. Patients will receive phototherapy treatments about 3 times per week for 12 weeks. They will then be observed for an additional 12 weeks. With each phototherapy treatment, patient response to prior phototherapy treatment will be collected by clinic staff or recorded on the phototherapy machine via patient assessment. Patients will complete a survey every 4 weeks for the duration of the study that captures patient reported outcomes.

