3.1.3 Observation Phase

The observation phase will start 84 days after the first treatment is received (or 14 days after randomization, whichever comes first) by the patient and will continue for an additional 84 days.

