4.4 Duration of Study Participation

The screening period is up to 28 days or longer based on the local practice standard of care. The total duration of participation after starting phototherapy is 168 days (i.e., intervention and observation periods). The total participation including the screening period is up to 196 days but could be longer as the screening period length will be determined by local standard of care.

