6.3 Observational Period (Weeks 13-24)

6.3.1 Week 16, 20 & 24

- Patient reported DLQI
- Patient reported target lesion image
- Patient reported psoriasis topical treatment
- Site reported oral and biologic psoriasis medications (at week 24)

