Duration of response will be measured in patients who achieved a DLQI score of 5 or less at week 12, are no longer receiving phototherapy, and who have not initiated a new systemic treatment or had dose escalation of an existing psoriasis systemic treatment at any point during the study. Duration of response will be defined as the length of time from week 12 to the earliest of DLQI > 5 or time of initiation of a new systemic treatment or dose escalation of an existing systemic treatment, with patients who maintain DLQI \leq 5 throughout the 12 week observation period with no new systemic treatments or dose escalation censored at week 24. In order to obtain results that are generalizable to the full ITT study population, we will use inverse probability weighting to account for possible selection bias due to differences between characteristics of participants included in this analysis and the full study population. Duration of response will be analyzed using a Cox proportional hazards regression model adjusted for treatment arm, skin type, and their interaction. Based on results for the interaction term between study arm and skin type, we will report differences in duration of treatment response between study arms by skin type.

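### Duration of response: starting or escalating systemic treatment in weeks 13–24 is both a bar to entering the analysis and one of its failure events

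*Combined protocol and SAP*

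**What the plan says.** The rules are in the duration-of-response paragraph of Section 8.2 (Secondary Endpoints).

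- **Entry.** Patients must have a DLQI of 5 or less at week 12, be off phototherapy, and be among those "who have not initiated a new systemic treatment or had dose escalation of an existing psoriasis systemic treatment at any point during the study".
- **Event.** The clock starts at week 12 and stops at "the earliest of DLQI > 5 or time of initiation of a new systemic treatment or dose escalation of an existing systemic treatment".
- **Censoring.** Patients whose DLQI stays at 5 or less, "with no new systemic treatments or dose escalation censored at week 24", are the censored group.
- **Weights.** Inverse probability weighting is to correct for selection "due to differences between characteristics of participants included in this analysis and the full study population".
- **Model.** A Cox model with treatment arm, skin type and their interaction.

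Other sections show how long the study lasts for a patient. Section 3.1.3 says the observation phase begins at day 84 "by the patient and will continue for an additional 84 days". Section 4.4 states: "The total duration of participation after starting phototherapy is 168 days (i.e., intervention and observation periods". Section 3.1 says: "Patients will complete a survey every 4 weeks for the duration of the study that captures patient reported outcomes", and Section 6.3.1 places those surveys at weeks 16, 20 and 24. Section 6.3.1 also lists "Site reported oral and biologic psoriasis medications (at week 24").

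**The concern.** The entry rule and the event rule apply to the same occurrence in the same period. A responder who starts or escalates systemic treatment in week 18, say, is a failure under the event definition and is not in the analysis set under the entry rule. Three things follow from the literal text:

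1. The systemic component of the event is empty, and the systemic clause in the censoring rule has no effect.
2. A responder whose DLQI rises above 5 at week 16 and who starts systemic treatment at week 20 is also removed, so a genuine DLQI event is lost.
3. Membership of the analysis set depends on events after time zero. Weights built on participant characteristics cannot repair this, because every patient with a later systemic start is removed and no one left in the set can stand in for that event.

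At stake is whether the analysis overstates how long response lasts, and whether a home-versus-office difference is hidden, exaggerated or created. Section 2.1 names duration of response in the primary objective, although Sections 2.2 and 3.2.2 list it as secondary.

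**Working it through.** **Comparison of windows.** The plan gives no event rate, hazard ratio or power for this endpoint, so there is no stated figure to reproduce. The first check is of the text.

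| Rule (Section 8.2) | Period covered |
|---|---|
| Exclusion for a systemic start or escalation | Whole study, which runs to day 168 (Section 4.4), i.e. week 24 |
| Failure by a systemic start or escalation | Week 12 to week 24 |
| Overlap | All of weeks 13–24 |

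The event window lies wholly inside the exclusion window, so the number of systemic failures in the analysis set must be zero.

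**Maintained response at week 24.** All rates here and below are assumptions. Per 100 week-12 responders, let D have DLQI above 5 first, S fail first by systemic treatment, and R be those of the D who start systemic treatment later.

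- By the event definition: (100 − D − S)/100
- By the literal entry rule: (100 − D − S)/(100 − S − R)

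With D = 30:

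| S | By definition | Literal, R = 0 | Overstated by (points) | Literal, R = 5 | Overstated by (points) |
|---|---|---|---|---|---|
| 2 | 68.0% | 68/98 = 69.4% | 1.4 | 68/93 = 73.1% | 5.1 |
| 5 | 65.0% | 65/95 = 68.4% | 3.4 | 65/90 = 72.2% | 7.2 |
| 10 | 60.0% | 60/90 = 66.7% | 6.7 | 60/85 = 70.6% | 10.6 |
| 20 | 50.0% | 50/80 = 62.5% | 12.5 | 50/75 = 66.7% | 16.7 |

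**Hazard ratio, home versus office.** Let relapse occur at weekly rate d and systemic starts, independent of relapse, at weekly rate s.

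- By the event definition: (d_home + s_home)/(d_office + s_office)
- By the literal entry rule: d_home/d_office

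| Scenario | By definition | Literal |
|---|---|---|
| d and s both equal by arm | 1.00 | 1.00 |
| d 0.03 office, 0.045 home; s 0.002 in both | 0.047/0.032 = 1.47 | 1.50 |
| d 0.03 office, 0.045 home; s 0.01 in both | 0.055/0.040 = 1.375 | 1.50 |
| d 0.03 in both; s 0.01 office, 0.02 home | 0.050/0.040 = 1.25 | 1.00 |

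Cox fits to simulated data (400,000 responders per arm, 12-week window) agreed within simulation error: 1.374 and 1.495 for the third row, 1.255 and 1.004 for the fourth. In the fourth row the literal rule removes 1 − exp(−0.12) = 11% of office responders and 1 − exp(−0.24) = 21% of home responders.

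**Starts only after relapse.** Take d = 0.03 in both arms, with systemic starts after relapse at 0.05 per week in office and 0.10 at home. The event definition gives a hazard ratio of 1.00 and maintained response of 70% in both arms. The literal rule removes 8% and 13% of responders. Maintained response becomes 76% (office) and 80% (home), and the simulated hazard ratio is about 0.78. With the arms swapped it is about 1.28.

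**The case against.** The ordinary reading removes the conflict. The entry sentence describes patients as they stand at week 12, and its verb tense can mean so far. The next sentence starts the clock at week 12 and treats later systemic starts as events, and the censoring clause would be redundant if entry already ruled them out. A programmer who applied the rule literally would find no systemic events and would probably ask why. The larger distortions also need assumptions that nothing in the documents supports: in the last scenario, about 8/30 and 13/30 of relapsers, roughly a quarter and more than two fifths, start systemic treatment within the window. Section 8.2 specifies a Cox model with an arm-by-skin-type interaction, not a week-24 maintained proportion or a single hazard ratio. It also compares four-weekly DLQI and week-24 changes in oral or biologic treatment between arms, so a difference in systemic use would still be reported.

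Much of this stands: judging entry at week 12 is probably what was meant, the harm arises only under literal coding, and it is small when starts are rare. But the objection infers the intent, while the written words cover the whole study and no section limits them to week 12. The week-24 medication report makes a whole-study flag easy to build. The separate comparisons do not supply a time-to-event result. Choosing between two readings once the data are in hand is what a pre-specified rule should prevent.

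**Conclusion.** The concern holds. As written, Section 8.2 contradicts itself on systemic starts and escalations after week 12. The literal rule empties one component of the event and selects patients on their later course, which the planned weights cannot correct.

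The size is unknown because the documents give no rates. Under the assumed rates, and only with literal programming, maintained response is overstated by 1.4 to 12.5 points when no relapser later starts systemic treatment, and by 5.1 to 16.7 points when 5 of 30 do. The hazard ratio is unchanged if systemic starts, before and after relapse, and DLQI relapse are all equal by arm. Otherwise it can move in either direction: slightly when starts are rare (1.47 to 1.50), or enough to hide a difference (1.25 to 1.00) or create one (1.00 to about 0.78 or 1.28).

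One secondary endpoint is affected. The co-primary analyses and the sample size are not. The correction should be made before the analysis is programmed.

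**What to change.** In the entry condition of Section 8.2, add the words 'up to week 12' after the quoted reference to the study, leaving the start of the window as it is. Keep initiation or escalation after week 12 as a failure event. Add one sentence stating that the inverse probability weights model eligibility as determined at week 12.

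One query goes with this. Confirm that the dates of systemic starts and escalations are recorded; Appendix D and the eCRF are not among the pages available, so this is not claimed as a gap. If only the week-24 report exists, state how a change first reported there is timed in the Cox model.

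The cost is one phrase and one sentence, plus a check of the eCRF. Visits, sample size and the co-primary analyses do not change.

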2.1 Primary Objective

To compare the effectiveness, safety (tolerability), and duration of treatment response at 12 weeks of home versus office-based NB-ultraviolet B phototherapy for the treatment of psoriasis

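### Section 8.2 prespecifies no overall home-versus-office effect on duration of response, and does not say how relapse times seen only at three surveys will be handled

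*Combined protocol and SAP*

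**What the plan says.** Section 2.1 states the primary objective as "To compare the effectiveness, safety (tolerability), and duration of treatment response at 12 weeks of home versus office-based NB-ultraviolet B phototherapy". Duration of response appears again among the secondary objectives (2.2) and endpoints (3.2.2).

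Section 8.2 gives it one model: "Duration of response will be analyzed using a Cox proportional hazards regression model adjusted for treatment arm, skin type, and their interaction". The fit is inverse-probability weighted and restricted to patients with DLQI of 5 or less at week 12 who are off phototherapy and have had no new or stepped-up systemic therapy. The reporting sentence says that, depending on the interaction result, "we will report differences in duration of treatment response between study arms by skin type".

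The event is the "earliest of DLQI > 5 or time of initiation of a new systemic treatment or dose escalation of an existing systemic treatment". Patients without an event are censored at week 24. The DLQI schedule after week 12 is "6.3.1 Week 16, 20 & 24". Section 8.2 agrees for the observation-period measures: "These measures will be assessed every four weeks during the observation period". Sites report oral and biologic medications at week 24 (6.3.1). No tie method, interval-censoring method or variance estimator is named for the Cox model.

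**The concern.** Two things are missing.

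First, in a model with an arm-by-skin-type interaction, the arm coefficient is the home effect in the reference skin type alone. The plan names no main-effects model, averaged contrast or standardized effect. Elsewhere it takes both steps: Section 8.1 estimates the overall effect on the primary endpoints from arm plus skin type with marginal standardization, and Section 8.2 tests heterogeneity in a separate interaction model. Duration has only the second step. An overall estimate chosen after the data are seen would not be prespecified, and the estimates that are prespecified are the least precise ones.

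Second, a continuous-time Cox model is specified for an outcome whose DLQI component can change only at three surveys. Many event times will be tied, and the hazard ratio then depends on how ties are handled.

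**Working it through.** **Plan's own figure.** None is given for duration: no event count, hazard ratio or power. The 175 per arm per skin type in Section 8.3 belongs to the binary primary endpoints. It reproduces: (1.96 + 0.842)² × (0.25 + 0.25) / 0.15² = 174.4, so 175 (power 80.1%). It says nothing about duration.

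**Step 1: what the model estimates.** Write log hazard = baseline + β·arm + γ₂S₂ + γ₃S₃ + δ₂·arm·S₂ + δ₃·arm·S₃. The arm effects are β, β + δ₂ and β + δ₃ in the three skin types. An overall effect would be, for example, β + w₂δ₂ + w₃δ₃, but the plan supplies no weights and no instruction to form it.

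**Step 2: precision.** With 1:1 arms, SE(log HR) ≈ 2/√events. Inputs:
- Enrolment of 350, 350 and about 80 (Section 3.1), total 780.
- 50% response (Section 8.3).
- 30% to 50% relapse over 12 weeks, an assumption because the documents give none.

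| Estimate | Events | SE(log HR) | Ratio to overall |
|---|---|---|---|
| Overall arm term | 117 to 195 | 0.185 to 0.143 | 1 |
| Type I/II, or III/IV | 52.5 to 87.5 | 0.276 to 0.214 | √(780/350) = 1.49 |
| Type V/VI | 12 to 20 | 0.577 to 0.447 | √(780/80) = 3.12 |

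The ratios do not depend on the response or relapse rates if these are equal across skin types. In type V/VI the 95% interval runs a factor of exp(1.96 × SE) = 3.1 to 2.4 either side of the estimate, against 1.44 to 1.32 overall. If all three groups reached 350, each ratio would be √3 = 1.73.

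**Step 3: grouped times.** Assume that every event is seen at a survey, the hazard is constant, the true hazard ratio is 1.5 and no weights are applied. Let q be office relapse per four weeks. Home relapse is p = 1 − (1 − q)^1.5, and office relapse over 12 weeks is 1 − (1 − q)³. With q and p the same in each interval:
- Breslow's large-sample score equation is solved by the risk ratio p/q.
- The exact-discrete method gives the odds ratio [p/(1 − p)] / [q/(1 − q)].
- Complementary log-log gives ln(1 − p)/ln(1 − q) = 1.5.
- Efron's score equation was solved numerically.

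| q | 12-week relapse | p | Breslow | Efron | Exact-discrete | Compl. log-log |
|---|---|---|---|---|---|---|
| 10% | 27% | 14.6% | 1.46 | 1.50 | 1.54 | 1.50 |
| 20% | 49% | 28.4% | 1.42 | 1.50 | 1.59 | 1.50 |
| 30% | 66% | 41.4% | 1.38 | 1.49 | 1.65 | 1.50 |
| 40% | 78% | 53.5% | 1.34 | 1.48 | 1.73 | 1.50 |

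A small simulation (40 replicates, 350/350/80 patients, half responding, 70% office relapse over 12 weeks) agrees: Breslow 1.361, Efron 1.480, complementary log-log 1.495 and ungrouped continuous times 1.492. At a true hazard ratio of 1, Breslow, Efron and exact-discrete all give 1.0.

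On the log scale the Breslow error is ln(1.5/1.462) = 0.026 at q = 10%, small beside the overall standard error in Step 2. At q = 40% it is ln(1.5/1.338) = 0.114, about one standard error, since 2/√(390 × 0.784) = 0.114 when the office rate is used for both arms.

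**The case against.** A reader might infer that the trial cannot say whether response lasts as long at home overall. The documents do not support that. A contrast or standardization of the fitted model would yield an overall effect. The reporting sentence can be read as conditional on the interaction result. Section 8.2 also says that all secondary analyses are repeated within skin type, which suggests an unstratified analysis comes first. And it plans a GEE comparison of dichotomized DLQI across the observation period in all skin types. These points stand as far as they go. None of them names a time-to-event contrast: the GEE covers all patients rather than week-12 responders, and the general reporting rule concerns means and frequencies.

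A reader might also infer that the Cox analysis is biased toward 1. That holds only under Breslow ties. Efron is nearly unbiased over the range examined, the exact-discrete method moves the estimate away from 1, and the plan names none of them. With no true difference nothing is distorted, and standard hypothesis testing, not non-inferiority, applies here.

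Nor do the documents show that almost all event times are tied. Starting or escalating systemic treatment is also an event with its own time, and the mix of events is not given.

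Finally, the larger standard errors are the ordinary price of subgroup estimates, and inference by skin type is a stated aim (Section 8.3). So those estimates are not a mistake. The gap is that nothing overall is planned beside them.

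**Conclusion.** The point holds as two omissions in Section 8.2. The overall duration effect that Section 2.1 calls for is not prespecified. The named estimates are about 1.5 or 3.1 times less precise than an overall arm term, provided events follow 350/350/80 enrolment. The handling of relapse times grouped at weeks 16, 20 and 24 is also unspecified. For a true hazard ratio of 1.5 and assumed 12-week relapse of 27% to 78%, the same plan wording admits 1.46 to 1.34 (Breslow) or 1.50 to 1.48 (Efron).

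The size of the second effect rests on assumed relapse rates, a constant hazard and all events falling at surveys. The inverse-probability weights were not modelled. The analysis should be amended, but the primary endpoint analyses are not affected.

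**What to change.** In Section 8.2:

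1. Define the overall duration comparison as the arm effect from a model with arm and skin type and no interaction, or as a standardized overall contrast with its weights stated.
2. Use a discrete-time complementary log-log model with an indicator for each four-week interval, or an interval-censored model. At minimum, keep Cox and name Efron ties.
3. Use a robust variance to allow for the inverse-probability weights.
4. Fit the arm-by-skin-type interaction in a second model, for heterogeneity and the by-skin-type estimates.

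The cost is SAP wording, with no new visits or data. The complementary log-log coefficient keeps its hazard-ratio interpretation. The downside is that a discrete-time model places any exactly dated systemic-treatment events into four-week intervals. If such dates are reliable and numerous, the interval-censored model is the better choice.
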